4.4 PATIENTS OF REPRODUCTIVE POTENTIAL

Pregnancy and breastfeeding are exclusion criteria for this study. It is important that female patients and the female partners of male patients do not become pregnant during the study and for a recommended period of 30 days after last dose of IMSA101.

Women of childbearing potential and male patients who are partners of women of childbearing potential must agree to use two forms of highly effective contraception during the study and for 30 days following the last dose of study drug. Highly effective contraception is defined as use of one or more methods that result in a low failure rate (i.e., less than 1%). The following are examples of acceptable methods of contraception: oral, injected, or implanted hormonal methods, intrauterine devices (IUD), condoms with spermicide product, vasectomy, or tubal ligation or occlusion.

A woman of childbearing or reproductive potential is defined as any female who has experienced menarche and who has not undergone successful surgical sterilization (hysterectomy, bilateral salpingectomy, or bilateral oophorectomy) or is not postmenopausal (defined as amenorrhea for at least 12 consecutive months with an appropriate clinical profile at the appropriate age, e.g., greater than 45 years).

A serum pregnancy test for all women of childbearing potential will be performed during screening. A pregnancy test will also be carried out at the End of Study (EOS) visit.

Female patients who become pregnant and male patients whose female partners become pregnant must report to the investigator and be removed from the study immediately.

5 STUDY PROCEDURES AND SCHEDULE

Study procedures will be performed as described in Section 3: Study Design and as shown in the Schedule of Assessments and Study Activities (Table 1 and Table 2).

5.1 DESCRIPTION OF STUDY DAYS AND STUDY TREATMENTS

5.1.1 Screening/Baseline (Day -30 to Day 1)

- Obtain written informed consent before the start of any study-specific procedures.
- Review inclusion and exclusion criteria.
- Complete medical history including all previous cancer treatments.
- Record concomitant medications including start dates, indication, dose, and frequency.
- Record demographic data including year of birth, current age, age when informed consent is signed, gender, race, and smoking status.
- Measure and record height (cm) and weight (kg).
- Record vital signs (blood pressure, respiration rate, heart rate, body temperature).
- Perform full physical examination.
- Perform neurologic examination.
- Assess and record ECOG performance status (Appendix 13.1).
- Perform a 12-lead ECG.
- Collect blood samples for hematology tests (including coagulation parameters and CBC with differential) within 72 h prior to Cycle 1 Day 1.
- Collect blood samples for serum chemistry tests and creatinine clearance (using the Cockcroft-Gault formula, Appendix 13.3) within 72 hours of Cycle 1 Day 1.
- Urinalysis
- Perform a serum pregnancy test for female patients of childbearing potential.
- Radiographic assessments and, if applicable, photographic assessments of skin lesions will be performed by a formal photography vendor at the same time points as the radiographic assessments. Detailed instructions for photography will be included in a photography manual.
- Collect archival tumor tissue, if available (Phase I only).

5.1.2 **Cycle 1 Day 1 (± 0 Days)**

• Record concomitant medications taken since screening including start dates, indication, dose, and frequency within 72 h prior to Cycle 1 Day 1.

- Measure and record weight (kg) within 72 h prior to Cycle 1 Day 1.
- Record vital signs (blood pressure, respiration rate, heart rate, body temperature) within 72 h prior to Cycle 1 Day 1.
- Perform neurologic examination within 72 h prior to Cycle 1 Day 1.
- Assess and record ECOG performance status within 72 h prior to Cycle 1 Day 1 (Appendix 13.1).
- Perform a 12-lead ECG 30 to 60 minutes post-dose.
- PK blood samples (Phase I monotherapy only). Detailed instructions outlined in the laboratory manual.
- PD blood samples (Phase I monotherapy and combo therapy). Detailed instructions outlined in the laboratory manual.
 - 24 h post-dose sample will require patient to return to clinic on Cycle 1 Day 2.
- PD tissue samples/biopsy of injected and non-injected tumor, if applicable (non-injected tumor biopsy required in at least 1 patient per cohort) (Phase I monotherapy and combo therapy). Core biopsies should be obtained; if not appropriate, biopsies via fine needle aspirate (FNA) or excision are permitted. Detailed instructions outlined in the laboratory manual.
- Administer study drug(s).
- Observe patient for 1 h following intratumoral injection.
- Assess and record AEs.
- Admit patient to the hospital for observation overnight. Patient may be released from the hospital when clinically indicated.

5.1.3 Cycle 1 Day 8 (+/- 3 Days)

- Record concomitant medications taken since the last visit including start dates, indication, dose, and frequency.
- Measure and record weight (kg).
- Record vital signs (blood pressure, respiration rate, heart rate, body temperature).
- Perform neurologic examination.
- Assess and record ECOG performance status (Appendix 13.1).
- Perform a 12-lead ECG 30 to 60 minutes post-dose.
- Collect blood samples for hematology tests (coagulation parameters, not required).
- Collect blood samples for complete serum chemistry.

- Administer study drug. For Cycle 1 Day 8 and Cycle 1 Day 15, IMSA101 doses should be administered no less than 4 days apart.
- Observe patient for 1 h following intratumoral injection.
- Assess and record AEs.

5.1.4 **Cycle 1 Day 15 (+/- 3 Days)**

- Record concomitant medications taken since the last visit including start dates, indication, dose, and frequency.
- Measure and record weight (kg).
- Record vital signs (blood pressure, respiration rate, heart rate, body temperature).
- Perform neurologic examination.
- Assess and record ECOG performance status (Appendix 13.1).
- Perform a 12-lead ECG 30 to 60 minutes post-dose.
- Collect blood samples for hematology tests (coagulation parameters, not required).
- Collect blood samples for serum chemistry tests.
- PD tissue samples/biopsy of injected and non-injected tumor, if applicable (non-injected tumor biopsy required in at least 1 patient per cohort) (Phase I monotherapy and combination therapy). Core biopsies should be obtained; if not appropriate, biopsies via FNA or excision are permitted.
- Administer study drug(s). For Cycle 1 Day 8 and Cycle 1 Day 15, IMSA101 doses should be administered no less than 4 days apart.
- Observe patient for 1 h following intratumoral injection.
- Assess and record AEs.

5.1.5 Day 1 (+/- 3 Days) of Each Subsequent Cycle

- Record concomitant medications taken since the last visit including start dates, indication, dose, and frequency.
- Measure and record weight (kg).
- Record vital signs (blood pressure, respiration rate, heart rate, body temperature).
- Perform neurologic examination.
- Assess and record ECOG performance status (Appendix 13.1).
- Collect blood samples for hematology tests (coagulation parameters, not required).
- Collect blood samples for complete serum chemistry.

- Administer study drug(s).
- Observe patient for 1 h following intratumoral injection.
- Assess and record AEs.
- PD blood samples (Phase I monotherapy and combo therapy). Samples to be collected predose Day 1 of Cycles 2 and 3.

5.1.6 Day 15 (+/- 3 Days) of Each Subsequent Cycle

- Record concomitant medications taken since the last visit including start dates, indication, dose, and frequency.
- Measure and record weight (kg).
- Record vital signs (blood pressure, respiration rate, heart rate, body temperature).
- Perform neurologic examination.
- Assess and record ECOG performance status (Appendix 13.1).
- Collect blood samples for hematology tests (coagulation parameters, not required).
- Collect blood samples for complete serum chemistry.
- PK blood samples (Phase I monotherapy patients but only if detectable signal was noted in Cycle 1 PK results)
- PD blood samples (Phase I monotherapy and combo therapy Cycle 2 Day 15)
- PD tissue samples/biopsy of injected and non-injected tumor, if applicable (non-injected tumor biopsy required in at least 1 patient per cohort) (Phase I monotherapy and combo therapy Cycle 2 Day 15 only). Core biopsies should be obtained; if not appropriate, biopsies via FNA or excision are permitted.
- Administer study drug(s).
- Observe patient for 1 h following intratumoral injection.
- Assess and record AEs.

5.1.7 End of Even-numbered Cycle (< 7 Days)

- Perform disease assessment according to RECIST Criteria (v1.1) (Appendix 13.2). In certain circumstances a patient experiencing RECIST progression of disease may be allowed to continue therapy on study where there is agreement between the investigator and sponsor that the patient is deriving clinical benefit.
- Radiographic assessments and, if applicable, photographic assessments of skin lesions will be performed by a formal photography vendor at the same time points as the radiographic assessments. Detailed instructions for photography will be included in a photography manual.

5.1.8 End of Treatment Visit

- Record concomitant medications taken since the last visit including start dates, indication, dose, and frequency.
- Measure and record weight (kg).
- Record vital signs (blood pressure, respiration rate, heart rate, body temperature).
- Perform and record full physical examination.
- Perform neurologic examination.
- Assess and record ECOG performance status (Appendix 13.1).
- Perform a 12-lead ECG 30 to 60 minutes post-dose.
- Collect blood samples for hematology tests (coagulation parameters, not required).
- Collect blood samples for complete serum chemistry.
- Perform a serum pregnancy test for female patients of childbearing potential.
- Perform disease assessment according to RESIST Criteria (v1.1) as described in Appendix 13.2. If applicable, photographic assessments of skin lesions will be performed. Perform a CT scan (or MRI or other appropriate assessment), if a recent scan within the past month is not available in the medical records.
- Assess and record AEs.

5.1.9 End of Study Visit (Safety Follow-up 30 days after Last Dose)

• Assess and record AEs.

5.1.10 **Cycle Extensions**

During this study, with the approval of the investigator and sponsor, a patient may be allowed a 2 week delay or extension between cycles. Rationale for delay or extension should be documented.

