2.2 SECONDARY OBJECTIVES

- Characterize the safety and tolerability of IMSA101 administered to cancer patients via intratumoral injections as monotherapy or in combination
- Identify and characterize preliminary signals of anti-tumor activity including overall response rate (ORR), duration of treatment response (DOR), time-to-tumor progression (TTP), and progression-free survival time (PFS)
- Characterize the PK of IMSA101 administered by intratumoral injection as monotherapy

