2.4.3 Secondary (Efficacy) Endpoints

Secondary efficacy endpoints may include:

- Response evaluation criteria in solid tumors (RECIST)-based objective response rate (ORR)
- Duration of response (DOR)
- Time to RECIST-based tumor progression (TTP)
- Progression-free survival time (PFS)

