13.2 RECIST GUIDELINE (VERSION 1.1)

All findings will be assessed for response according to RECIST v1.1 criteria (Eisenhauer, 2009) at the end (\leq 7 days) of every even numbered cycle (Cycle 2, Cycle 4, etc.), and EOT. Refer to Section 6.9 for details.

RECIST v1.1 criteria do not mention including or excluding lesions that are being biopsied or injected. However, for the purposes of this protocol, the injected and biopsied lesions are to be captured as non-target lesions only (Phase I only), as follows:

- Injected and biopsied lesion = non-target lesion #1
- Non-injected and biopsied lesion = non-target lesion #2 (if applicable)

All patients will have their BEST RESPONSE on study classified as outlined below:

Complete Response (CR)

Disappearance of all target lesions. Any pathological lymph nodes (whether target or non-target) must have reduction in the short axis to < 10mm.

Partial Response (PR)

At least a 30% decrease in the sum of diameters of target lesions, taking as reference the baseline sum LD.

Stable Disease (SD)

Steady state of disease. Neither sufficient shrinkage to qualify for PR nor sufficient increase to qualify for PD.

Progressive Disease

At least a 20% increase in the sum of diameters of measured lesions taking as references the smallest sum of diameters recorded since the treatment started. In addition to the relative increase of 20%, the sum must also demonstrate an absolute increase of at least 5 mm. Appearance of one or more new lesions will also constitute progressive disease.

Response Duration

Response duration will be measured from the time measurement criteria for CR/PR (whichever is first recorded) are first met until the first date that recurrent or progressive disease is objectively documented, taking as reference the smallest measurements recorded since the treatment started.

Stable Disease Duration

Stable disease duration will be measured from the time of start of therapy until the criteria for progression are met, taking as reference the smallest measurements recorded since the treatment started.

Target lesions	Non-Target lesions	New Lesions	Overall response
CR	CR	No	CR
CR	Non-CR-Non-PD	No	PR
CR	NE	No	PR
PR	Non-PD/ or not all evaluated	No	PR
SD	Non-PD/ or not all evaluated	No	SD
Not all evaluated	Non-PD	No	NE
PD	Any	Yes or No	PD
Any	PD	Yes or No	PD
Any	Any	Yes	PD

Evaluation of Best Overall Response – Patient with Target (+/- non-target) disease

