Evaluation of Best Overall Response – Patient with Non-Target Disease

Non-Target lesions	New Lesions	Overall response
CR	No	CR
Non-CR-Non-PD	No	Non-CR/Non-PD
Not all evaluated	No	NE
Unequivocal PD	Yes or No	PD
Any	Yes	PD

Note: Patients with a global deterioration of health status requiring discontinuation of treatment without objective evidence of disease progression at that time should be reported as "*symptomatic deterioration*". Every effort should be made to document the objective progression even after discontinuation of treatment.

Method of Measurement

The same method of assessment and the same technique should be used to characterize each identified and reported lesion at baseline and during follow-up.

Clinical Lesions

Clinical lesions will only be considered measurable when they are superficial (e.g., skin nodules, palpable lymph nodes). For the case of skin lesions, documentation by color photography including a ruler to estimate the size of the lesion is recommended.

Chest X-ray

Lesions on chest X-ray are acceptable as measurable lesions when they are clearly defined and surrounded by aerated lung. However, CT is preferable.

CT / MRI.

CT and MRI might be the best currently available and reproducible methods to measure target lesions selected for response assessment. Conventional CT and MRI should be performed with cuts of 10 mm or less in slice thickness contiguously. Spiral CT should be performed using a 5 mm contiguous reconstruction algorithm. This applies to the chest, abdomen and pelvis. Head & neck and extremities usually require specific protocols.

Ultrasound

When the primary endpoint of the study is objective response evaluation, ultrasound should not be used to measure tumor lesions that are clinically not easily accessible. It is a possible alternative to clinical measurements for superficial palpable nodes, subcutaneous lesions and thyroid nodules. Ultrasound might also be useful to confirm the complete disappearance of superficial lesions usually assessed by clinical examination.

Cytology / Histology

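### DOR, TTP and PFS are planned, but nothing scheduled after End of Treatment records progression, even for the symptomatic-deterioration patients whom Appendix 13.2 says to keep following

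*Combined protocol and SAP*

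**What the plan says.** **Endpoints.** Section 2.2 names "duration of treatment response (DOR), time-to-tumor progression (TTP), and progression-free survival time (PFS") among the preliminary activity signals. Section 2.4.3 lists the same measures under "Secondary efficacy endpoints may include". Appendix 13.2 defines response duration, which ends at objectively documented progression or recurrence. PFS and TTP are not defined beyond their names.

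**Assessments.** Appendix 13.2 places RECIST assessment at the end of "every even numbered cycle (Cycle 2, Cycle 4, etc.), and EOT". Tables 1 and 2 agree: disease assessment is marked at screening, end of even cycles and EOT, and the End of Study (EOS) column is marked for adverse events only. At EOT, Section 5.1.8 says "Perform disease assessment according to RESIST Criteria (v1.1) as described in Appendix 13.2", but a new scan is needed only "if a recent scan within the past month is not available in the medical records".

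**After EOT.** Section 5.1.9, "End of Study Visit (Safety Follow-up 30 days after Last Dose", contains one task, the recording of adverse events. The table footnotes describe this 30-day visit as the final assessment.

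**Appendix instruction.** The note on symptomatic deterioration in Appendix 13.2 covers patients who stop because their health has declined without objective progression. It ends: "Every effort should be made to document the objective progression even after discontinuation of treatment".

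**Analysis.** Section 10.1.1 defers methods to a SAP still to be written. Section 10.3.8 plans no imputation. No censoring rule for DOR, TTP or PFS appears anywhere.

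**The concern.** Section 7.1 lists many reasons to stop treatment without documented progression: adverse events, intercurrent illness, patient request, non-compliance, and sponsor or investigator request. After EOT, such a patient has no scheduled observation that could yield a progression date. The only scheduled source for a date of death is adverse-event reporting, which ends 30 days after the last dose.

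The symptomatic-deterioration group matters most. These patients stop because they are getting worse, they do not count as RECIST progression, and they have no later scan. If they are censored at the last assessment, the Kaplan-Meier curve treats them as having the same outlook as patients still on treatment.

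Section 10.1.1 says the final SAP will set criteria for signal detection and for comparison with standard-of-care benchmarks. The study is non-randomised, so there is no concurrent arm in which the same bias would cancel. The SAP can set rules later, but it cannot supply dates that the case report form never requested.

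**Working it through.** The documents give no median, event count or dropout rate for these endpoints, so there is no figure to reproduce. The check has a trace of the documents and two illustrations with assumed inputs.

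**1. What each endpoint needs and what is scheduled after EOT**

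| Needed | Scheduled source after EOT |
|---|---|
| Progression date (TTP, PFS, DOR) | None |
| Death to day 30 (PFS) | SAE reporting, Section 9.1.2 |
| Later death, possibly study-related | Notification, Sections 9.1.5 and 9.2.1 |
| Later death, not study-related | None |
| Start of new anti-cancer therapy | None |

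**2. Size if events are censored one scan early**

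From the documents: assessment every second 28-day cycle, so 2 × 28 = 56 days, or 8 weeks.

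Assumed: exponential progression times; a share *f* of 15–25% of events censored at the scan before the one that would have shown progression.

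Let *q* be the chance of progressing within one 8-week interval. Of those entering an interval, *fq* are removed at its start, 1 − *fq* remain at risk, and *q*(1 − *f*) have recorded events. The Kaplan-Meier factor is

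1 − *q*(1 − *f*)/(1 − *fq*) = (1 − *q*)/(1 − *fq*).

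Over two intervals the reported 16-week PFS is *S*/(1 − *fq*)², where *S* = (1 − *q*)² is the truth. If the EOT scan catches half of these events (assumed), *f* is halved.

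| True *S* | *q* | *f* = 0.15 | *f* = 0.25 | Half caught: *f* = 0.075 | Half caught: *f* = 0.125 |
|---|---|---|---|---|---|
| 25% | 0.500 | 0.25/0.925² = 29.2% | 0.25/0.875² = 32.7% | 0.25/0.9625² = 27.0% | 0.25/0.9375² = 28.4% |
| 50% | 0.293 | 0.50/0.956² = 54.7% | 0.50/0.927² = 58.2% | 0.50/0.978² = 52.3% | 0.50/0.963² = 53.9% |

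**3. Direction**

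Assumed: on-treatment median of 4 months, so λ = ln 2/4; a share *f* of 10%, 20% or 30% stopping without progression, so the stopping hazard is λd = λ*f*/(1 − *f*); and a hazard after stopping of *h* × λ. Censoring at EOT estimates exp(−λ*t*), which at 6 months is 35.4% in every case. The true value is

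exp(−(λ+λd)*t*) + ∫₀ᵗ λd exp(−(λ+λd)*u*) exp(−*h*λ(*t*−*u*)) d*u*.

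| *h* | True 6-month PFS at *f* = 10 / 20 / 30% | Bias of the reported 35.4% |
|---|---|---|
| 0.5 | 36.6 / 38.0 / 39.6% | Downward |
| 1 | 35.4 / 35.4 / 35.4% | None |
| 2 | 33.9 / 32.2 / 30.3% | Upward |
| 4 | 32.6 / 29.6 / 26.2% | Upward |

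The sign depends entirely on how patients fare after stopping.

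**4. Scale in one arm**

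With 20 patients per Phase IIA arm (Section 3.1.2), the same shares of 10–30% are 2–6 patients. The binomial standard error is √(0.25 × 0.75/20) = 9.7 points at 25% and √(0.5 × 0.5/20) = 11.2 points at 50%.

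**The case against.** **Bias is not established.** No censoring rule exists and the SAP is still to come, so informative censoring is an inference. Patients who leave by request or for non-compliance need not have a worse outlook. This stands. A reader might infer that PFS and TTP will be overstated; the documents support only that they may be.

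**The appendix sentence is narrow.** It sits inside the note on symptomatic deterioration and is a best-effort instruction. A reader might take it to cover every early stop, but it does not address toxicity, withdrawal or new therapy. This also stands.

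**Some capture exists.** EOT requires a RECIST assessment, and a new scan if none exists from the past month. Section 5.1.11 allows unscheduled visits with any procedure. Sections 9.1.5 and 9.2.1 ask for later deaths that may be study-related. So it would be wrong to say that deaths after day 30 are simply not collected, and nothing shows that PFS would collapse into TTP, since deaths on treatment and to day 30 are captured. These routes are discretionary or limited to related events, however, and none captures progression systematically.

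**The first illustration is near a worst case.** It assumes every censored patient would have progressed at the next scan. The columns with half caught at EOT soften this. A reader might also infer that the median shifts by a whole scan interval. That happens only when the true median falls near a scan time. With a true 12-week median, *q* = 1 − 2^(−8/12) = 0.370, and reported 16-week PFS is 0.397/(1 − 0.370*f*)², or 44.5% at *f* = 0.15 and 48.2% at *f* = 0.25. Both are below 50%, so the estimated median stays at the 16-week scan.

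**Materiality is limited.** The endpoints are secondary, Section 2.4.3 says only that they may be included, Phase IIA is mainly descriptive, and the sampling error in one arm exceeds the illustrated bias. This supports a moderate grade. It does not remove the point: sampling error is reported with the estimate, whereas this bias would go unseen.

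**Conclusion.** The point holds in limited form and should be addressed. For patients who stop with symptomatic deterioration, Appendix 13.2 asks for progression to be documented after discontinuation, and no scheduled visit or data field implements it. For other stops without progression there is a gap. Deaths more than 30 days after the last dose that are not study-related are not systematically captured.

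If such patients are censored at their last assessment, the possible upward bias in 16-week PFS is about 4–8 points (29–33% against 25%; 55–58% against 50%) with no rescue at EOT, and about 2–4 points (27–28%; 52–54%) if the EOT scan catches half. These figures rest on assumed exponential times and an assumed 15–25% of events censored one scan early. The bias is zero if the hazard after stopping is unchanged and reverses if it is lower. DOR shares the gap, but its size has not been estimated. No general claim about the median is supported, and the primary MTD/RP2D endpoint is unaffected.

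**What to change.** 1. Align Section 5.1.9 and the EOS column of Tables 1 and 2 with Appendix 13.2. For patients who stop without documented progression, record the progression date, date of death and start of new anti-cancer therapy available from routine records.
2. In the SAP, state the main censoring rule and pre-specify a PFS/TTP sensitivity analysis that counts discontinuation for symptomatic deterioration as an event. As a further sensitivity analysis, also count the start of new anti-cancer therapy as an event. This requires symptomatic deterioration to be a recorded stopping reason; the list in Section 7.1 does not name it.
3. Tabulate patients censored without progression by reason. Section 7.1 already requires the reason for withdrawal on the eCRF.

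The cost is one extra analysis and a record-review field, with no added scan or visit. The downside is that progression dates from routine records are less standardised than scheduled RECIST assessments, so they should be flagged as such in the data and the report. This is a partial remedy: it makes the uncertainty visible but does not replace scheduled assessment.
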